	
 2. BNP area under curve (AUC) from Day 1 (baseline) until Day 28 [Visit 1 Day 1 – Visit 4 Day 28]. 3. NT-pro-BNP area under curve (AUC) from Day 1 (baseline) until Day 28 [Visit 1 Day 1 – Visit 4 Day 28]. 4. Incidence of fatal outcomes (cardiac and non-cardiac) during 12-month follow-up period [Visit 1 Day 1 – Visit 6 Day 365]. 5. Incidence of hospitalizations due to HF or other cardiac reasons not associated with HF, or due to non-cardiac reasons during 12-month follow-up period [Visit 1 Day 1 – Visit 6 Day 365]. 6. Incidence of new cases of HF (defined as hospitalization due to HF or new onset of HF) during 12-month follow-up period [Visit 1 Day 1 – Visit 6 Day 365]. 7. Incidence of “fatal outcome (due to any reason) or hospitalization due to HF or new onset of HF” during 12-month follow-up period [Visit 1 Day 1 – Visit 6 Day 365]. 8. Incidence of “fatal outcome (due to any reason) or hospitalization due to HF” during 12-month follow-up period [Visit 1 Day 1 – Visit 6 Day 365]. 9. Changes in levels of BNP and NT-pro-BNP during 12-month follow-up period compared to baseline [Visit 1 Day 1 – Visit 6 Day 365]. 10. Changes in structural and functional echocardiographic parameters after 12 months compared to baseline [Visit 1 Day 1 – Visit 6 Day 365]. 
Exploratory endpoints:
 
 1. Changes in concomitant therapy [Visit 1 Day 1 – Visit 6 Day 365]. 2. Interaction between STEMI outcomes and peculiarities of coronary bed lesion based on baseline CAG results [Visit 1 Day 1 – Visit 6 Day 365].
Safety evaluation	
Safety endpoints:
 
 1. Frequency of AE/SAE during the study. 2. Changes in physical examination (including body weight), vital signs during the study.
Statistical analysis	
Statistical analysis will be performed in the following populations.
 
Full Analysis Set (FAS):
 
Full analysis set for efficacy analysis will include all randomized subjects, who received the study products and underwent at least one CRP measurement after administration of the study products. This set is the main population for efficacy analysis.
 
Per Protocol Set (PPS):
 
All FAS subjects without relevant Protocol deviations affecting assessment of the primary efficacy parameter. Such major Protocol deviations will be defined before database lock in a blinded data

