9.2. Selection of data for the analysis

Statistical analysis will be conducted in the following study sets:

Full analysis set (FAS) for the efficacy analysis

Full analysis set (FAS) for efficacy analysis will include all randomized subjects who received the study products and underwent at least one hsCRP measurement after administration of the study products. This set is the main population for efficacy assessment.

Per Protocol Set (PPS)

ProtocolAll FAS subjects without important Protocol deviations affecting assessment of the primary efficacy parameter. Such Protocol deviations will be defined before breaking the blind in a blinded data review. This set is supplementary population for efficacy assessment.

Safety set

All randomized patients who have received the study drugs.

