9.3.3. Efficacy analysis

9.3.3.1. *Analysis of primary endpoint*

Primary endpoint is hsCRP area under curve (AUC) from Day 1 (baseline) until Day 14 [Visit 1 Day 1 – Visit 3 Day 14].

The following hypotheses will be tested for each RPH-104 dose level:

Null hypothesis H0: difference between mean $AUC_{1-14\text{ days}}$ CRP in RPH-104 group and mean $AUC_{1-14\text{ days}}$ CRP in placebo group is equal to 0.

Two-sided alternative hypothesis H1: difference between mean $AUC_{1-14\text{ days}}$ CRP in RPH-104 group and mean $AUC_{1-14\text{ days}}$ CRP in placebo group is different from 0.

Individual $AUC_{1-14\text{ days}}$ CRP values will be calculated using trapezoidal method. Mean $AUC_{1-14\text{ days}}$ CRP value will be compared between RPH-104 and placebo groups using analysis of variance ANOVA. Mean AUC values for RPH-104 80 mg, RPH-104 160 mg and placebo groups, differences in mean values and relevant two-sided 95% confidence intervals (CI) and well as p -values will be presented.

All hsCRP concentration values by study visits will also be presented as lists.

9.3.3.2. *Analysis of secondary endpoints*

- hsCRP area under curve (AUC) from Day 1 (baseline) until Day 28 [Visit 1 Day 1 – Visit 4 Day 28].
- BNP area under curve (AUC) from Day 1 (baseline) until Day 28 [Visit 1 Day 1 – Visit 4 Day 28].
- NT-pro-BNP area under curve (AUC) from Day 1 (baseline) until Day 28 [Visit 1 Day 1 – Visit 4 Day 28].

Analysis will be done similar to the analysis of the primary endpoint described above.

- Incidence of fatal outcomes (cardiac and non-cardiac) during 12-month follow-up period [Visit 1 Day 1 – Visit 6 Day 365].
- Incidence of hospitalizations due to HF or other cardiac reasons not associated with HF, or due to non-cardiac reasons during 12-month follow-up period [Visit 1 Day 1 – Visit 6 Day 365].
- Incidence of new cases of HF (defined as hospitalization due to HF or new onset of HF) during 12-month follow-up period [Visit 1 Day 1 – Visit 6 Day 365].
- Incidence of “fatal outcome (due to any reason) or hospitalization due to HF or new onset of HF” during 12-month follow-up period [Visit 1 Day 1 – Visit 6 Day 365].
- Incidence of “fatal outcome (due to any reason) or hospitalization due to HF” during 12-month follow-up period [Visit 1 Day 1 – Visit 6 Day 365].

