9.7. Interim analysis

After the last subject completes 28-day follow-up period, an interim analysis of hsCRP, BNP and NT-pro-BNP will be performed after 14 and 28 days of the study. Based on this analysis, decision on the study termination will not be taken. The analysis results may be used to define the strategy for further RPH-104 development.

Population for performing an interim analysis – Full Analysis Set.

During the interim analysis the primary efficacy analysis will be performed (see section 9.3.3.1). This analysis will be performed only once and will not be repeated during the final analysis stage. Sensitivity analysis can't be done during the interim stage and will be performed during the final analysis stage.

Secondary efficacy variables (AUC from day 1 to day 28) will be derived and analysed for parameters hsCRP, BNP and NT-pro-BNP at the interim analysis stage (see section 9.3.3.2). This analysis will be performed only once and will not be repeated during the final analysis stage.

Values at visits (Day 1 – baseline, Days 3, 14 and 28) and changes from baseline (Days 3, 14 and 28) will be described for hsCRP, BNP and NT-pro-BNP parameters using descriptive statistics supported with graphics.

All individual subject's data will be kept blinded for the Sponsor and all other staff involved into the data review except unblinded statistician.

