12.4. Database management and quality control

In the studies using eCRFs the Sponsor (or appointed CRO) representatives will analyze the data entered by the site personnel for accuracy and completeness. In case of discrepancies or missing values, queries for data will be generated specifying the nature of the issue and required clarification. These queries will be forwarded to the study site. The appointed study site officer is required to provide responses to the queries and make any necessary amendments immediately.

By the end of the study, any Protocol deviations will be determined. By the end of these actions and confirmation of database completeness and accuracy, it will be locked and prepared for data analysis.

After database lock, the Investigator will receive a CD or paper version of subject data for archiving in the study site.

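### The summary and section 9.2 set different deadlines for Per Protocol Set exclusions, and neither ties sign-off to the Day 28 primary analysis, about 11 months before the only database lock described

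*Combined protocol and SAP*

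**What the plan says.** Two current texts set the deadline for PPS exclusions.

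- Protocol summary, statistical analysis row: "Such major Protocol deviations will be defined before database lock in a blinded data" (the sentence ends with the word review).
- Section 9.2: "Such Protocol deviations will be defined before breaking the blind in a blinded data review".

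Both describe the PPS as supplementary to the FAS, and both limit exclusions to deviations that affect assessment of the primary parameter, hsCRP AUC from Day 1 to Day 14.

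The timing of the primary analysis is in section 9.7: "After the last subject completes 28-day follow-up period, an interim analysis of hsCRP, BNP and NT-pro-BNP will be performed", and "During the interim analysis the primary efficacy analysis will be performed (see section 9.3.3.1"). It is done once, on the FAS, and not repeated at the end; sensitivity analysis is left to the final stage. Section 9.3.3.1 gives the form of the output: "Mean AUC values for RPH-104 80 mg, RPH-104 160 mg and placebo groups, differences in mean values", with confidence intervals and p-values. On use of the interim results, section 9.7 says "The analysis results may be used to define the strategy for further RPH-104 development". On blinding it says "All individual subject's data will be kept blinded for the Sponsor and all other staff involved into the data review except unblinded statistician".

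Section 12.4 says "By the end of the study, any Protocol deviations will be determined", and places the database lock after that step. No other lock is described.

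**The concern.** A per-protocol analysis supports the main analysis only if its membership was fixed without regard to the result. Deciding which deviations matter enough to exclude a subject involves judgement, so the decision should come before anyone involved can know how the comparison turned out.

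Where a trial has a single analysis after a single lock, the summary's deadline and that of section 9.2 are the same moment and the difference in wording is harmless. This trial analyses its primary endpoint well before study end. The summary's deadline therefore falls after the by-arm result has been produced, and section 9.2 can be read either way. If membership is settled in that interval, agreement or disagreement between the PPS and FAS results is weaker evidence than it appears.

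**Working it through.** The plan states no figure for the interval between the two deadlines, so there is none to reproduce. The check is a comparison of the texts and calendar arithmetic.

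**Inputs**

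- Trigger for the primary analysis: last subject's Day 28 ± 3 (section 9.7; Table 1).
- End of follow-up: last subject's Month 12 ± 2 weeks, nominally Day 365 (section 4.2.1; Table 1).
- Lock: after the end-of-study deviation check (section 12.4).
- Planned durations: recruitment 9 months, clinical part 22 months (summary).
- Conversion: 30.44 days per month.

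**Interval from the Day 28 trigger to the end of follow-up**

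- Nominal: 365 − 28 = 337 days; 337 / 30.44 = 11.1 months.
- Shortest with visit windows: (365 − 14) − (28 + 3) = 351 − 31 = 320 days = 10.5 months.
- Longest with visit windows: (365 + 14) − (28 − 3) = 379 − 25 = 354 days = 11.6 months.
- From the planned durations: 22 − 9 − 28 / 30.44 = 12.1 months.

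Two lags are not stated: from Day 28 to the interim result, and from the last visit to lock. They act in opposite directions. Assuming each lies between 0 and 2 months, the interval from result to lock is roughly 11.1 − 2 = 9.1 to 11.1 + 2 = 13.1 months.

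**What each rule permits**

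| Rule | Latest date for PPS decisions | Time after the Day 28 trigger (nominal, lags ignored) |
|---|---|---|
| Summary | End-of-study lock | about 11 months |
| 9.2, blind broken when codes are used for the Day 28 analysis | Before that analysis | none |
| 9.2, blind broken at final unblinding | End of study | about 11 months |

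**Does anything else force an early decision?** The interim population is the FAS and sensitivity analysis is deferred, so the Day 28 stage can be completed without a PPS list. No PPS review is scheduled for that stage.

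**Could the decision be made early?** The deviations in question concern AUC to Day 14. With Visit 3 in its window they have occurred by Day 14 + 3 = 17, before the earliest in-window Visit 4 at Day 28 − 3 = 25. Some may be discovered only later, through monitoring or source verification.

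**Who could know the result?** Section 9.7 protects individual subject data. Nothing restricts the aggregate by-arm result, and its stated use in development strategy suggests that it leaves the unblinded statistician. That last step is an inference.

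**The case against.** The strongest reply is that the plan already has the essential safeguard. Both texts require a blinded review, and section 9.7 withholds individual data from the sponsor and the data reviewers. A reader might infer that the summary allows exclusions made with arms known, and might try to size the harm by removing the least favourable subjects from one arm. The documents do not support this. It would need knowledge of each subject's arm and exclusion by outcome, whereas the plan blinds the reviewers and requires a protocol deviation. An aggregate mean does not tell a reviewer which arm a subject is in. This part of the reply stands in full.

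The two deadlines are also compatible: a team that fixes the PPS before the first analytical use of treatment codes satisfies both. That is true on one reading of section 9.2. The section does not say that this is the reading intended, and no order of precedence between it and the summary is given.

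A reader might also take section 12.4 as a third PPS rule. It is a general data-management statement covering deviations over the whole study and does not mention the PPS. It matters here only because it locates the lock.

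Finally, section 9.1 defers detail to a statistical analysis plan, so an earlier data cut or PPS sign-off could be specified there. That cannot be excluded, but section 9.1 requires that plan to be final only by database lock, so it does not itself secure an earlier date.

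**Conclusion.** The point holds in limited form. The summary and section 9.2 give deadlines that, in this trial, can lie about 11 months apart (337 days nominal; 320 to 354 with visit windows). Section 9.2 leaves open which unblinding it means. On the summary's rule, and on one reading of section 9.2, blinded reviewers could settle PPS membership after the aggregate by-arm primary result exists.

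The consequence is confined to the supplementary PPS analysis. The FAS primary result and the sample size do not change, and the documents give no basis for putting a number on any bias in the PPS estimate.

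The conclusion rests on two assumptions: that the end-of-study lock is the only one, since no other is described, and that the aggregate result may reach those who review deviations, since no text prevents it. If either were shown to be wrong, the matter would reduce to aligning the wording.

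**What to change.** State one rule in the summary and in section 9.2: deviations that exclude a subject from the PPS are determined, and the PPS list is signed off, at a blinded data review held before treatment codes are released to the unblinded statistician for the Day 28 analysis. Afterwards the list changes only for documented data errors or for deviations discovered late, with each change decided blind to treatment and reported. Section 12.4 needs only a cross-reference to this rule.

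The cost is wording in two sections, one cross-reference, and one blinded review brought forward with the data cleaning that it depends on. No additional data are collected.

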2.1. Introduction

The term "myocardial infarction" (MI) is used when there is verified myocardial lesion (defined as increased cardiac troponin level by at least one value exceeding 99th percentile of normal reference value) and myocardial necrosis in clinical situations suggesting myocardial ischemia. To ensure urgent selection of treatment approach including reperfusion therapy, MI is diagnosed in cases of anginal pain or its equivalents with ST elevation in at least 2 or more consequent leads or acute left bundle branch block (LBBB) and defined as ST-segment elevation MI (STEMI) ([Ibanez B. et al, 2017](#)).

Coronary heart disease (CHD) is the leading cause of mortality globally (1.8 million deaths annually) and is 20% of all fatal outcomes in Europe despite relevant variations between the countries ([Ibanez B. et al, 2017](#)).

Epidemiological data in the RF are disparate. According to the available assessments, in Russia economic losses from all cardiovascular diseases (CVD) in 2016 was 2.7 trillion rubles being equivalent to 3.2% of GDP. In the structure of losses among all circulatory diseases, CHD rates the first, financial burden in Russia is more than 1 trillion rubles (Kontsevaya A.V. et al, 2018).

One of the most relevant forms of CHD characterized by high mortality is MI. Globally more than 15 million of new onset MI cases are reported annually ([Garganeyeva A.A. et al, 2015](#); [WHO, 2017](#)). MI aggravates prognosis significantly: according to European register, mortality among the subjects with STEMI during hospitalization varies from 4% to 12%, 6-month mortality may exceed 12%, 12-month mortality is approximately 10% and may reach 20% within 5 years ([Ibanez B. et al, 2017](#)). At that, unfavourable prognosis is still relevant for surviving post-MI subjects ([Berger C.J., 1992](#); [VNOK Work Group, 2007](#); [Minzdrav, 2016](#)).

According to some authors, the urgency of MI epidemiological situation is determined by its frequency among the population aged > 60 years old both by morbidity and mortality parameters and by hospital and pre-hospital lethality ([Okrugin S.A., 2018](#)).

The main therapeutic measures are directed at myocardial reperfusion as soon as possible with recanalization by percutaneous coronary intervention (PCI) ([Ibanez B. et al, 2017](#)).

Despite significant progress in MI therapy, more than 20% surviving subjects develop HF (HF) within 90 days ([Gjesing A. et al., 2014](#)).

According to Russian epidemiological studies (EPOHA-CHF, EPOHA-Hospital-CHF and EPOHA-Decompensation-CHF), prevalence of chronic HF in the RF increased from 4.9% (1998) to 10.2% (2014) within 16 years. At that, the number of subjects with chronic HF functional class (FC) II-IV increased significantly due to increased age of the subjects as well as increased weight of etiological CHD causes (69.7% in 2014) and previous MI (15.3% in 2014). Overall mortality is 6% annually ([Fomin I.V., 2016](#)).

STEMI is associated with intensive inflammatory response promoting further lesion and predicting increased mortality or HF risk ([Frangogiannis N.G., 2008](#); [Velagaleti R.S. et al., 2008](#); [Vanhaverbeke M. et al., 2018](#)).

Interleukin-1 (IL-1) is the key mediator of local and systemic inflammatory response to injury. Nonclinical studies demonstrated that IL-1 inhibition improves infarction healing and prevents the development of HF ([Abbate A. et al., 2006](#)).

The studies indicated that concentration of high-sensitive C-reactive protein (hsCRP), the marker of inflammatory response and surrogate marker of IL-1 activity, in subjects with acute coronary

syndrome/MI, independently correlated with the risk of unfavourable cardiovascular outcomes (including HF) ([Ridker P. et al., 2005](#); [Scirica B.M., 2009](#); [Vanhaverbeke M. et al., 2018](#)). Individual studies also demonstrated that, where the signs of persistent inflammation (increased hsCRP level) and hemodynamic stress (an increase in a proBNP level) are observed, the subjects are under the highest risk of HF ([Scirica B.M., 2009](#); [Vanhaverbeke M. et al., 2018](#)).

Currently evaluation of medicinal products blocking activity of IL-1 (anakinra, rilonacept, canakinumab) is performed to improve outcomes in subjects with acute coronary syndrome/MI ([Buckley L.F. and Abbate A., 2018](#)).

Randomized double-blind placebo-controlled study of canakinumab (CANTOS) enrolled 10061 subjects with MI and hsCRP level of ≥ 2 mg/L. The subjects received 50 mg, 150 mg or 300 mg of canakinumab or placebo subcutaneously every 3 months. It was demonstrated that, after a single administration of the product, the subjects reaching reduced hsCRP below 2 mg/L showed reduced frequency of major adverse cardiovascular events by 25% and mortality by 31% compared to the subjects not reaching hsCRP reduction. Similar results were demonstrated for other outcomes (including hospitalization due to unstable angina requiring unscheduled revascularization ([Ridker P.M. et al., 2017](#); [Ridker P.M. et al., 2018](#)).

Three pilot clinical studies of anakinra for STEMI were carried out: VCU-ART, VCU – ART2 and VCU-ART3 ([Abbate A. et al., 2010](#); [Abbate A., 2013](#), [Abbate A. et al., 2020](#); [Van Tassell B.W. et al., 2018](#)). In total, these pilot studies enrolled 140 subjects with STEMI receiving reperfusion therapy who were randomized (within 12 hours post coronary angiography) for daily anakinra therapy for 14 days. Anakinra, a recombinant human IL-1 receptor antagonist (IL-1RA), was tolerated well and reduced serum hsCRP level. Anakinra-treated subjects showed tendency for more favourable left ventricular (LV) remodelling and lower frequency of HF in the mid-term and long run.

RPH-104 belongs to the class of target agents affecting IL-1. It is a hybrid protein selectively binding and inactivating IL-1 β . Nonclinical studies show that RPH-104 is being developed for the treatment of human subjects with diseases associated with increased activity of IL-1 β .

To date, the clinical study of drug use in treatment of acute gout attacks has been completed, and the studies of potential benefits of the drug for the treatment of Familial Mediterranean fever, idiopathic recurrent pericarditis are ongoing.

Given similar mechanism of action of RPH-104 and anakinra, RPH-104 is expected to reduce intensity of inflammatory response at myocardial lesion in subjects with STEMI and, therefore, to reduce hsCRP level and improve short-term and long-term outcomes.

2.2. Cumulative presentation of the results of nonclinical and clinical studies relevant for this study

RPH-104 is a hybrid protein with a molecular weight of the non-glycosylated form of 126.8 kilodalton (kDa) selectively binding and inactivating IL-1 β . Two active parts of the molecule are responsible for RPH-104 binding with IL-1 β : an extracellular portion of human IL-1 receptor type 1 (IL-1R1), type 1 and a portion of human IL-1 receptor accessory protein (IL-1RAcP) that is an IL-1 co-receptor.

Structurally, RPH-104 molecule contains two polypeptide chains: the first one consists of extracellular part of IL-1 receptor (amino acids from 18 to 333 of human IL-1R1) and mutant Fc-fragment of human immunoglobulin G1 (IgG1); the second one consists of the part of IL-1RAcP (amino acids from 21 to 358 of human IL-1RAcP) and mutant Fc-fragment of human IgG1. Each of the extracellular parts of the molecule also contains 7 covalently bound glycans, and each of Fc-

fragments carries one glycan.

RPH-104 is a highly active inhibitor of IL-1 β -mediated signal pathway.

Investigation of inhibitory effect of RPH-104 on IL-1 β -mediated secretion of IL-6 cell line of non-transformed human lung fibroblasts (MRC5) demonstrated that 50% inhibitory concentration of RPH-104 (IC₅₀) is about 0.4 ng/mL (2.0 pmol/L).

The amino acid sequence of the extracellular domain of IL-1 receptor in the RPH-104 molecule subunit is 94.7% identical to the amino acid sequence of IL-1 receptor of cynomolgus monkeys and only 64% identical to the IL-1R1 sequence of rodents. In addition, RPH-104 has comparable cross-reactivity in tissues of humans and cynomolgus monkeys. Therefore, cynomolgus monkeys are a suitable biological species for nonclinical studies of RPH-104 *in vivo*.

RPH-104 shows linear pharmacokinetics (PK) in animals and humans. After a single subcutaneous administration to cynomolgus monkeys, RPH-104 bioavailability is 52-85% without signs of accumulation. After repeated administration to cynomolgus monkeys, plasma concentration and half-life tended to decrease by 20-80% compared to single dose values due to production of anti-product antibodies. Apparent gender-related differences in the product PK are lacking.

RPH-104 toxicity has been studied in mice and monkeys. Clinical symptoms and abnormal laboratory values during 4-week study of the product were mild and reversible in most animals by the end of recovery period. No cases of product-related animal mortality were reported in this study. In a 26-week RPH-104 repeated dose nonclinical study on cynomolgus monkeys, cases of serious toxicity requiring early euthanasia were reported. The cases recorded were considered as related to immunosuppressive mechanism of action of RPH-104 as an IL-1 β antagonist. Immunosuppression on the background of long-term administration of high doses of RPH-104 is due to inhibition of IL-1 β and meets the purpose of RPH-104 administration for the treatment of autoinflammatory diseases.

The medicinal product has immunogenic properties in monkeys.

The results of repeated dose toxicity studies with weekly subcutaneous 4-week administration suggest that RPH-104 no adverse effect level (NOAEL) in mice and monkeys was 100 mg/kg.

Mathematic modeling studies demonstrated that the minimum effective dose of RPH-104 required to achieve the desired plasma level of free IL-1 β was 1 mg upon once weekly dosing. Maximum tolerated dose (MTD) for humans is 6.4 mg/kg which is equivalent to 384 mg based on a 60 kg body weight.

Nonclinical studies on the model of acute MI were not performed.

Given its mechanism of action, RPH-104 is designed for investigation and use in humans for the treatment of autoinflammatory diseases associated with increased activity of IL-1 β .

In 2018, the first clinical study (phase 1) of RPH-104 was completed. The study aimed at evaluating the tolerability, safety, pharmacokinetics, pharmacodynamics and immunogenicity of the drug (RPH104FIH01/CL04018045) in healthy volunteers. The study results demonstrated that RPH-104 at doses from 4 to 160 mg inclusive with a single subcutaneous injection are tolerated well by the volunteers of either gender. No serious adverse events (SAEs) or any other adverse events (AEs) resulting in early withdrawal have been reported. All adverse events (70 in total) in all dose groups were mild and resolved completely without any complications. Headache was the only AE with tendency for higher frequency in RPH-104 group compared to placebo.

The results of investigation of RPH-104 PK after a single administration presented in analysis of this clinical study demonstrated linear and dose-dependent increase in C_{max} and AUC_(0-t) values. In general, median T_{max} was 96 hours (4 days), however the median was 120 hours (5 days) in 40 and 160 mg groups. Half-life was similar in all dose groups and was equivalent to 235-249 hours (10

CONFIDENTIAL

Translation dated 27-Oct-2021

based on Russian Version 4.0 dated 02-Oct-2021

Page 31 of 98

days).

The results of pharmacodynamic (PD) study presented in the RPH104FIH01/CL04018045 study report demonstrated that administration of the product at 4 to 160 mg did not cause any significant changes in IL-1 α or IL-1 β levels in healthy volunteers. The changes in the level of CRP were regarded as normal fluctuations. Volunteers receiving RPH-104 showed increased IL-1RA levels due to the time post dosing starting from 20 mg dose which was not observed in placebo group. This trend towards an increase in the IL-1RA levels over time after the product administration was noted at all dose levels. Such increase in IL-1RA level is considered as an additional benefit, potentially capable of increasing RPH-104 efficacy without increasing the drug-related safety risks. Nevertheless, this requires confirmation in further studies. The volunteers in the study did not show any relevant product-related changes in IL-6 levels associated. During the study, there were no signs of the effect of RPH-104 on S100 A8 levels.

No antibodies to RPH-104 were detected in the blood samples of healthy volunteers collected during the study.

In 2020, an international multicenter randomized double-blind adaptive placebo-controlled single-dose study to evaluate the efficacy and safety of ollokizumab (IL-6 inhibitor) and RPH-104 in patients with severe COVID-19 (SARS-CoV-2) infection conducted in RF was completed (CL04041078). The analysis of primary efficacy endpoint (response to treatment) showed no significant differences between the treatment groups.

During the study of RPH-104 administration, 128 AEs were reported in 61 (49.6%) patients in the RPH-104 group and 111 AEs in 48 (38.7%) patients in the placebo group. The most common AEs belonged to the systemic organ class of "Investigations" (ALT increased, AST increased, GGT increased): 29 (23.6%) patients in the RH-104 group and 23 (18.5%) patients in the placebo group. Less common AEs belonged to the SOC of "Infections and infestations" (e.g. acute sinusitis, bacterial bronchitis, COVID-19, *C. difficile*-induced pseudomembranous colitis, otitis media, otosalpingitis, pneumonia, pseudomembranous colitis, sepsis, septic shock, urinary tract infection, fungal urinary tract infection, viral sepsis – none of events were reported in more than 5% in each treatment group).

At least one SAE was reported in 12.2% of patients in the RPH-104 group and 6.5% of patients in the placebo group. The majority of SAEs belonged to the SOC "Infections and infestations" (i.e. sepsis, septic shock, COVID-19, viral sepsis). SAEs that led to death were reported in 11.4% and 4.8% of patients in the RPH-104 and placebo groups, respectively. Only one SAE that resulted in death in the RPH-104 group was considered related to the study drug (i.e. a case of septic shock). RPH-104 was generally well-tolerated by patients. No new safety signals related to the use of RPH-104 were identified. It should be noted that no cases of death have been reported in any other ongoing studies of RPH-104 so far.

In 2021, an open-label randomized phase 2a clinical study assessing the safety, tolerability, pharmacokinetics and pharmacodynamics of RPH-104 at various doses in subjects with an acute gout episode in the RF (CL04018054) was completed. In this study, the subjects received RPH-104 at single subcutaneous doses of 4 mg, 20 mg, 40 mg, 80 mg, or 160 mg, control subjects received diclofenac orally for 12 days.

The most pronounced decrease in the joint pain severity 72 hours after the start of the study treatment (primary endpoint) was observed in the RPH-104 20 mg, 80 mg and 160 mg dose groups, as well as the diclofenac group. In all groups, the use of the study treatment resulted in decreased severity of swelling and pain in the affected joint, elimination of erythema and improvement of the patients' performance status. The results of analysis of changes in the health assessment parameters (using the HAQ) indicated clinically significant improvement of the patients' performance status while on

CONFIDENTIAL

Translation dated 27-Oct-2021

based on Russian Version 4.0 dated 02-Oct-2021

Page 32 of 98

the study treatment in the 20 mg, 40 mg, 160 mg dose groups, and the diclofenac group.

The analysis of PK parameters in this study demonstrated a tendency to increased C_{max} and AUC with the drug dose increased, except for the 20 mg dose group, which demonstrated higher mean values of these parameters, similar to those observed in the 80 mg dose group. High interindividual variability of T_{max} was observed. The half-life in the dose groups was about 10 days.

RPH-104 dosing in patients with acute gout attacks resulted in decreased concentrations of the main inflammatory markers – hsCRP and serum amyloid A (SAA). hsCRP and SAA levels tended to show more significant decrease in the RPH-104 80 mg and 160 mg dose groups; the 80 mg dose group also demonstrated a statistically significant superiority in respect of hsCRP level increase compared to the diclofenac group.

The study demonstrated a favorable safety profile of the drug. AEs related to the use of RPH-104 included: in the 40 mg dose group – injection site hemorrhage, gouty arthritis; in the 80 mg group – drug-induced liver injury; in the 160 mg group - leukocytosis, sinus tachycardia, injection site erythema, injection site itching, cholesterol level increased, creatinine level increased, triglyceride level increased, blood urea level increased, lymphocyte count increased, creatinine clearance decreased, neutrophil count and percentage decreased, arthralgia, joint swelling, pain in extremities, allergic dermatitis. Injection site reactions were observed only in three patients treated with RPH-104: two patients in the 4 mg dose group (swelling, hemorrhage) and one patient in the 160 mg dose group (injection site erythema and itching).

